3.2.7 Clinical Laboratory Measurements

Laboratory testing (hematology, urinalysis, serum chemistry, virology, serology, pregnancy tests, PD, PK, and anti-drug antibodies [ADA]) will be performed using established methods by a central laboratory.

Abnormalities in clinical safety laboratory tests that are considered clinically significant are to be recorded on the AE eCRF page. Laboratory results will be graded using the NCI CTCAE, Version 4.03.

3.2.8 Pregnancy Testing

Pregnancy testing will be performed for women of childbearing potential. Urine or serum test is acceptable; however, positive urine tests must be confirmed with serum testing.

3.2.9 Virology

Testing for hepatitis C antibody, hepatitis B surface antigen, and HIV antibody will be performed at screening.

3.2.10 Serum Tetanus Antibody and Varicella-Zoster Virus Antibody Testing

Samples for serum tetanus antibody and Varicella-Zoster virus antibody testing are to be collected.

3.2.11 Pharmacokinetics (PK) Sampling

The following PK parameters will be studied in Cohort 1: $t_{1/2}$, C_{max} , T_{max} , AUC_{0-24} , and $AUC_{0-\infty}$. For all successive cohorts, the PK parameters studied will be maximum serum concentration of SYNT001 and the associated T_{max} . Specific collection times are detailed in [Table 5](#).

3.2.12 Pharmacodynamic Sampling

PD samples will be collected for analyses throughout the study. Measurements for PD biomarkers (albumin levels, hematocrit, hemoglobin, platelet count, reticulocyte count, LDH, and total and indirect bilirubin) will be derived from the clinical safety laboratory results. Samples for each type of PD will be collected according to the schedule shown in [Table 6](#).

3.2.13 Immunogenicity Testing

SYNT001 is being developed for the acute and chronic therapy of autoimmune disorders. Although SYNT001 is a humanized IgG4 monoclonal antibody, exposure to SYNT001 in clinical trials could result in the development of ADAs, with potential consequences ranging from neutralization or lessening of drug efficacy to safety consequences such as allergic reactions.

Testing will first detect binding ADAs, then, for all confirmed positive samples, a titer will be determined and there will be testing for neutralizing antibodies using a validated cell based assay.

3.2.14 Circulating Immune Complexes

Patients with autoimmune diseases such as WAIHA frequently have elevated levels of CICs as part of their autoimmune disease process. In these patients the degree of elevation may correlate with disease activity. In the SYNT001 phase 1a single dose escalation healthy volunteer study, almost all baseline CIC results were within the normal range. Treatment with a single IV dose of SYNT001 resulted in a dose-dependent decrease of up to 50% in CICs. CICs are most frequently assessed using either a C1q-based binding assay (ELISA), or less frequently by binding to Raji Cells via their complement receptor (Flow Cytometry).

3.2.15 Direct Antiglobulin (Coombs) Test

WAIHA is caused by autoantibodies (usually IgG) that bind to RBC antigens. This results to the activation of the complement system and deposition of complement protein C3 on the RBCs. Red blood cells coated with IgG with or without complement disposition are removed from the circulation by the reticuloendothelial system in the spleen and liver leading to anemia via a process known as extravascular hemolysis. The direct antiglobulin, or Coombs, test is used to determine whether a patient's RBCs are coated with IgG and/or complement proteins. Anti-IgG and anti-C3 antisera are added to a patient's red cells, and if IgG or C3 are present the RBCs clump or agglutinate, which is detected visually.

3.2.16 Quantitative Coombs Assay

Subject and control RBC-bound IgG, IgM and C3 will be measured by flow cytometry. RBCs coated with serial dilutions of monoclonal anti-Rh(D) IgG and IgM serve as positive controls. Quantum™ MESF (Molecules of Equivalent Soluble Fluorochrome) microsphere beads

coated with known numbers of fluorescent dye molecules are used as internal validation markers prior to analysis. Dynabeads® Protein G are used to quantify binding of mouse anti-human IgG, IgM and C3 antibodies. Binding of IgG is expressed as the geometric mean of the fluorescence intensity.

3.2.17 Study Drug Administration

Subject in Cohort 1 will receive SYNT001 10 mg/kg weekly x 5 doses.

Subjects in Cohort 2 will receive SYNT001 10, 20 or 30 mg/kg weekly x 3 doses (Loading), followed by SYNT001 10, 20 or 30 mg/kg every other week x 5 doses (Maintenance). The Maintenance dose frequency may be increased to weekly (Cohort 2 alternative weekly maintenance schedule).

SYNT001 will be given as a 250-mL IV infusion over 1 hour ±15 minutes using a 0.2-micron, inline filter.

3.2.18 Adverse Event Assessments

Information regarding the occurrence of AEs will be collected from the time the subject signs the informed consent form and continuing through the last study visit. Findings at screening and Day 0 (pre-dose) will be recorded as medical history. Any known untoward event that occurs beyond the AE reporting period that the Investigator assesses as related to study drug also should be reported as an AE. Clinical AEs will be graded using the NCI CTCAE, Version 4.03.

3.2.19 Prior and Concomitant Medications

Prior to protocol amendment 5, all medications a subject received within 14 days prior to enrollment through the end of the study were documented. A history of treatments taken for primary disease, even if not taken within the 14 days prior to enrollment, were collected. After protocol amendment 5, all WAIHA treatments and all other treatments a subject receives within at least 3 months prior to screening through the end of study will be documented.

4. STATISTICAL METHODOLOGY

All descriptive and inferential statistical analyses will be performed using Statistical Analysis System (SAS®) software Version 9.3 or higher.

Phoenix WinNonlin Version 6.4 or higher will be used in the determination of the PK terminal phase and the calculation of PK parameters. PK parameters will be calculated via SAS and verified with the Phoenix WinNonlin results.

Missing data will not be imputed unless otherwise stated. All clinical data captured will be provided in data listings.

4.1 General Design

All clinical data captured will be provided in data listings. Subject disposition, demographic information, and baseline characteristics will be presented. Results will be summarized by dose and dosing regimen (cohort), and in total. Any discrepancy between treatment to be given and treatment received will be accounted for in these displays.

Continuous data will be described using descriptive statistics: number of observations (n), mean, standard deviation (SD), median, Q1 (25th percentile), Q3 (75th percentile), minimum, and maximum. Geometric mean (GM) and GM CV will be provided for PK parameters.

Categorical data will be summarized using frequencies and percentages. When categorical data are presented, the percent will be suppressed when the count is zero to draw attention to the non-zero counts. The denominator for all percentages, unless otherwise specified, will be the number of subjects in the specified analysis population.

4.2 Analysis Populations

Three sub-populations will be employed in the analysis of study data:

- The **Safety population** will consist of all subjects who have received at least one dose of study drug.
- The **PK population** will consist of all subjects who receive at least one dose of study drug and have post-dose PK data available. PK concentrations and parameters will be summarized based on the PK population.
- The **PD population** will consist of all subjects who receive at least one dose of study drug and have post-dose PD data available. PD data will be summarized based on the PD population.

Primary safety analyses will be performed on the Safety population. Demographics, subject disposition, and screening and baseline characteristics will be summarized for the Safety, PK and PD populations, where appropriate.

4.3 Subject Disposition

Counts and percentage of subjects who are in each study population (Safety, PK and PD populations), who complete the study, and who withdraw early from the study will be presented by cohort and in total. The primary reasons for early withdrawals will also be tabulated.

Subject disposition, inclusion / exclusion criteria and comments will be listed.

A listing of all screen failures (i.e., subjects who were screened but not enrolled) will be presented along with reasons for screen failure.

4.4 Demographics and Baseline Characteristics

Demographics and baseline characteristics will be summarized descriptively by cohort and in total for the Safety population and repeated for PK and PD populations if they are different from the Safety population.

Demographic and baseline characteristics include, but are not limited to, age at informed consent, gender, race, ethnicity, body weight, and body mass index (BMI), age at diagnosis of WAIHA, WAIHA disease duration, and Karnofsky Performance Scale score (%).

Continuous variables (e.g., age, weight, and BMI) will be summarized by descriptive statistics. Categorical variables (e.g., gender, race, and ethnicity) will be summarized by the number and percentage of subjects in corresponding categories.

Baseline is defined as the Day 0 (pre-dose) measurement. If missing, the last measurement prior to the first study drug administration will be used as the baseline value.

Medical/surgical history will be coded using the Medical Dictionary for Regulatory Activities (MedDRA 19.1) and summarized for the number and percentage for each System Organ Class (SOC) and preferred term by cohort and in total for the Safety Population. Hematologic variables history will also be summarized. All medical/surgical history and hematologic variables history will also be listed.

A summary table for categories of protocol deviations will be produced for major protocol deviations. Protocol deviations will also be listed for the Safety population.

4.5 Prior and Concomitant Medications

All medications administered during the study will be listed and coded using the most current version of WHO Drug Dictionary (WHO Drug Sept 2016E B2).

For prior or concomitant medications, incomplete (i.e., partially missing) start date and/or stop date will be imputed. When the start date and the stop date are both incomplete for a subject, impute the start date first. See [Appendix B](#) for details on imputation rules.

A listing of all concomitant medications including the reported term, preferred term, and Anatomical Therapeutic Chemical (ATC) class, start and stop dates, and other relevant data will be provided.

The number and percentage of patients taking, prior medications, concomitant medications, and medication for potential infusion-related reactions (IRRs) will be summarized by cohort, ATC class, and preferred term. Concomitant medications include all medications taken on or after the first dose of the study drug. Prior medications include all medications taken before the first dose of study drug.

4.6 Study Medication Administration

Dose administered (mg/kg), percentage of total dose administered (%), total administration time (minutes), volume administered (mL) and number of vials used will be summarized at each scheduled visit by cohort.

Percentage of total dose administered (%) = total dose administered / planned total dose * 100%.

Study medication administration data will be listed.

4.7 Safety Analyses

All statistical analysis of safety outcomes will be descriptive. Safety observations and measurements include AEs, treatment-emergent AEs (TEAEs), SAEs, safety laboratory tests, vital sign measurements, PEs, and ECGs. The incidence of AEs, TEAEs and SAEs will be summarized by cohort, severity and relationship to study product. Baseline for safety parameters is defined as Day 0 (pre-dose) measurement. If missing, the last measurement prior to the first study drug administration will be used as the baseline value.

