4.7.1 Adverse Events

Adverse events data will be coded using the Medical Dictionary for Regulatory Activities (MedDRA 19.1). Adverse events will be graded using the NCI CTCAE, Version 4.03.

A treatment-emergent adverse event (TEAE) is defined as any AE that starts on or after the first dose of study drug or occurs prior to the first dose and worsens in severity on or after the first dose of study drug, during the treatment period and follow-up period.

For AEs with partial start dates, non-missing date parts will be used to determine if the AE is treatment-emergent or not. If a determination cannot be made using the non-missing date parts as to when the AE occurred relative to study drug administration, e.g. AE start year and month are the same as the year and month of the first dose of investigational product, then the AE will be classified as treatment-emergent. See [Appendix B](#) for details on imputation rules.

An overview of TEAEs will be provided. The overview will summarize the subject incidence of the following information:

- Any TEAEs
- Worst NCI CTCAE grade of TEAEs
- Drug-related TEAEs
- Worst NCI CTCAE grade of drug-related TEAEs
- Any study drug-related Grade 3 or greater TEAEs
- TE-SAEs
- Drug-related TE-SAEs
- TEAEs leading to discontinuation of study drug
- Drug-related TEAEs leading to discontinuation of study drug
- TEAEs leading to study drug interruption
- Drug-related TEAEs leading to study drug interruption
- TEAEs leading to study drug dose reduction
- Drug-related TEAEs leading to study drug reduction
- Death

TEAEs will also be summarized using SOC, preferred term and SOC, preferred term and severity grade based on NCI CTCAE (Version 4.03). Drug-related TEAEs will be summarized in the same manner. IRR related AEs will be summarized separately.

The incidence and percentage of subjects with at least 1 occurrence of a preferred term will be included, using the most severe grade. The number of events per preferred term will also be summarized. Causality (relationship to study drug) will be summarized separately.

TEAEs, SAEs, deaths and AEs leading to withdrawal, dose reduction, dose interruption, or treatment discontinuation will be listed. Duration of AEs will be determined and included in listings, along with action taken and outcome.

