4.9.2 Blood Transfusions

The number of units of packed red blood cells received by subjects will be summarized by cohort.

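### Adverse event incidence, event counts and red-cell units are whole-study figures by cohort, with no rate per infusion or per subject-time to set against unequal planned exposure

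*SAP*

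**What the plan says.** The primary endpoint in both documents is safety summarized by dose and dosing regimen. The SAP carries it out as follows.

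- **SAP 4.7:** "The incidence of AEs, TEAEs and SAEs will be summarized by cohort, severity and relationship to study product".
- **SAP 4.7.1:** an event counts as treatment-emergent if it starts or worsens on or after the first dose, "during the treatment period and follow-up period". Subject incidence is tabled by preferred term, and "The number of events per preferred term will also be summarized". For infusion-related reactions, "IRR related AEs will be summarized separately"; no per-infusion rate is stated.
- **SAP 4.1:** "Results will be summarized by dose and dosing regimen (cohort), and in total", and "The denominator for all percentages, unless otherwise specified, will be the number of subjects in the specified analysis population".
- **SAP 4.9.2:** "The number of units of packed red blood cells received by subjects will be summarized by cohort". No visit or period is named, and the matching objective covers transfusions during the study, so I read this as a whole-study figure.
- **SAP 4.6:** dose given, percentage of total dose, "total administration time (minutes), volume administered (mL) and number of vials used will be summarized at each scheduled visit by cohort". The percentage of total dose is relative to the planned total.

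I found no rate per infusion or per subject-time, and no common observation window, in either document. The mock-up tables are stand-alone documents (SAP 6) and were not available.

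**The concern.** The tables will set regimens side by side, and the regimens differ in planned exposure. A subject with more infusions and a longer treatment period has more chances to have an event, so two regimens with equal risk per infusion or per day are expected to show different crude percentages.

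The dosing summary does not make up for this. Infusions per cohort could be summed from the number of subjects at each visit, but the SAP does not turn that into a rate. Because percentage of total dose is relative to plan, complete courses of 5, 8 and 13 infusions would all read 100%. Time on study per subject is not summarized. It can also vary within a cohort: a subject who withdraws for a reason other than an AE may be replaced (SAP 5), yet stays in the Safety population after one dose (SAP 4.2).

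At stake is how the only output for the primary endpoint can be read. No error rate or formal test is involved.

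**Working it through.** **Planned exposure** (SAP 3.1; Protocol 4.4 and the visit schedules)

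| | Cohort 1 | Cohort 2 | Cohort 2, weekly option |
|---|---|---|---|
| Infusions | 5 | 3 + 5 = 8 | 3 + 10 = 13 |
| Days from first dose | 28 + 84 = 112 | 84 + 56 = 140 | 140 |
| Treatment share | 28/112 = 25% | 84/140 = 60% | 60% |

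Ratios to Cohort 1 are 8/5 = 1.6 (or 13/5 = 2.6) for infusions and 140/112 = 1.25 for days. The counts match the dosing days in the schedules.

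The 112 and 140 days apply to TEAEs. AEs and SAEs are collected from consent, so their window is up to 14 + 112 = 126 against 28 + 140 = 168 days. Protocol 4.4 prints a maximum of 154 days for Cohort 2, but its own parts give 28 + 84 + 56 = 168. I use the sum; the table needs correcting in any case.

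**Crude incidence under equal risk.** The documents give no event risks, so the per-infusion risk p is an assumption. With constant, independent and identical risk, incidence after n infusions is 1 − (1 − p)^n.

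| p | n = 5 | n = 8 | n = 13 |
|---|---|---|---|
| 2% | 9.6% | 14.9% | 23.1% |
| 5% | 22.6% | 33.7% | 48.7% |

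With 8 and 12 subjects, exact binomial probabilities that Cohort 2 shows the higher percentage, for p = 2% to 5%, are:

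- 8 against 5 infusions: 0.61 to 0.68 (Cohort 1 higher: 0.31 to 0.25; the rest are ties).
- 13 against 5: 0.78 to 0.87.
- 5 against 5, for reference: 0.44 to 0.47.

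**What narrows the gap** (mean risk 5%)

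- *Subjects differ in risk.* Take a beta distribution with a + b = 5, so a = 0.25 and b = 4.75. Incidence is 1 − Π(b + i)/(a + b + i) for i = 0 to n − 1. This gives 17.3% and 22.9% for 5 and 8 infusions, a gap of 5.6 points instead of 33.7 − 22.6 = 11.1.
- *Dosing stops for another event.* If events A and B each have 5% risk per infusion and A ends dosing, incidence of B is 0.05 × (1 − 0.9025^n)/0.0975, where 0.9025 = 0.95². This gives 20.6%, 28.7% and 37.8% for n = 5, 8 and 13.
- *Risk confined to early infusions.* If it all lies in the first five, the gap is zero. Prophylaxis after a first reaction also shrinks it.

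**Red-cell units.** At an equal daily rate, expected units per subject differ 1.25-fold.

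**Why a single subject-month rate is not enough.** Set the treatment rate to 1 per 28 days and the follow-up rate to f in both cohorts. Unsplit rates are (1 + 3f)/4 in Cohort 1 and (3 + 2f)/5 in Cohort 2.

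- f = 0.5: 0.625 against 0.80, ratio 1.28.
- f = 0.25: 0.4375 against 0.70, ratio 1.60.

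The boundary matters too. Adding 7 days after the last infusion moves the treatment shares to 35/112 = 31% and 91/140 = 65%.

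**Worst laboratory grade.** The schedule grids give 9 draws after Day 0 in each base cohort. In Cohort 1, 4 of 9 fall in the treatment period (Days 7, 14, 21, 28). In Cohort 2, 7 of 9 do (Days 7, 14, 28, 42, 56, 70, 84). Footnote d of the Cohort 2 schedule speaks of all study visits, which would add Day 112.

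**The case against.** The strongest reply is that the number of infusions is part of the regimen, so crude incidence by regimen is what the endpoint asks for. Safety analysis is descriptive (SAP 4.7), no statistical analysis supports dose-escalation decisions (SAP 7), and the sample size was set by feasibility (SAP 5). Dosing and TEAEs are listed, and early withdrawals are tabled by cohort, so with at most 20 subjects anyone could derive rates later.

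Most of this stands, and it limits the point to an addition. It does not remove the point: rates derived later would use a denominator and period boundary chosen after open-label data had been seen.

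Four stronger readings are tempting, and the documents do not support them.

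- *The planned safety comparison is biased.* No between-cohort test or estimate is planned, and crude incidence is correct for a full course.
- *Stopping a subject after a first event leaves incidence unchanged.* That holds for one event type only. SAP 4.7.1 tables incidence by preferred term, and stopping for one event removes later chances of another. Cohort halts and study-wide suspension (Protocol 8.5) act in the same direction.
- *Equal numbers of draws protect worst laboratory grade.* The split of 4 of 9 against 7 of 9 shows they do not.
- *The corticosteroid table has the same fault.* It is by cohort and visit (SAP 4.9.3), so it is a separate, smaller matter. That it would count steroids given for infusion reactions is inferred from the SAP's silence; the objective itself is limited to steroids for WAIHA.

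**Conclusion.** The point holds as an inexpensive improvement. The SAP's whole-study summaries by cohort, with subjects as denominator, do not let a reader separate more risk from more exposure when planned infusions are 5 against 8 or 13 and post-first-dose observation is 112 against 140 days. That difference in planned exposure comes straight from the documents and is certain.

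The size of its effect is not. The 22.6%, 33.7% and 48.7% rest on an assumed equal, constant and homogeneous 5% risk per infusion. Under the assumed beta spread, the figures for 5 and 8 infusions fall to 17.3% and 22.9%. Cohort 2 may also receive a different mg/kg dose, so equal per-infusion risk is itself only a reference case. Nor would Cohort 2 be certain to look worse: even under homogeneous equal risk, Cohort 1 shows the higher percentage with probability 0.25 to 0.31.

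**What to change.** Keep the crude tables and add to the SAP, by regimen received:

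1. Number of infusions received and time on study per subject.
2. The separate summary of infusion-related reactions, also expressed per infusion given.
3. Other TEAEs and SAEs, and red-cell units, per subject-month, split into treatment and follow-up, with one boundary rule stated in advance for all cohorts.

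If Cohort 2 uses more than one regimen, say that cohort in SAP 4.1 means regimen received. Add a footnote that worst on-study laboratory grade needs the same caution.

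A separate minor addition concerns SAP 4.9.3. Show corticosteroid use for WAIHA on its own, using the reason for use already recorded (Protocol 6.10), and label visits by time since last infusion. A discretionary taper may start 14 days after the last dose. At Day 112 it has therefore been allowed for 112 − 42 = 70 days in Cohort 1 and 112 − 98 = 14 in Cohort 2. Cohort 1 Days 56 and 84 pair with Cohort 2 Days 112 and 140 (28 and 56 days since last infusion).

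The cost is a few derived columns and footnotes from data already collected. The drawback is imprecision. With 8 × 5 = 40 and 12 × 8 = 96 planned infusions, illustrative counts of 2/40 (5.0%) and 5/96 (5.2%) have exact 95% intervals of 0.6% to 16.9% and 1.7% to 11.7%, treating infusions as independent. The rates stay descriptive and do not separate schedule from mg/kg dose or from sequential enrolment.

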A semi-mechanistic model of FcRn-IgG interactions and FcRn inhibition with SYNT001 was jointly developed by Applied BioMath and the Sponsor. The model was designed to simulate PK and PD responses to various dosing regimens of SYNT001 to inform clinical trial design. Initial simulations were able to capture both PK and PD responses to single doses of SYNT001 from a single-ascending dose study in healthy volunteers and predict multiple dose responses from ongoing studies with good fidelity. The model predicted an IgG reduction of approximately 75% by Day 33, which was determined to be acceptably close to the actual mean IgG reduction of 59% by Day 30 observed in patients. Subsequent iterations of the model have used patient data from ongoing patient studies to further calibrate dose responses. In the most recent simulations, multiple dosing scenarios have been explored, including responses to weekly, bi-weekly, and loading doses. A simulated dosing regimen consisting of three weekly loading doses of 30 mg/kg SYNT001 followed by every other week maintenance doses of 10 mg/kg SYNT001 achieved a nadir IgG reduction of approximately 78% between Days 21 and 28 and maintained an IgG reduction between approximately 50% and 68%. This level of total IgG reduction has been associated with clinical efficacy in early studies of SYNT001-treated pemphigus subjects, and represents a target for future studies in other indications. This regimen of 30 mg/kg loading doses and 10 mg/kg maintenance doses was determined to be the optimal starting regimen to achieve meaningful IgG reduction while maximizing patient safety. Future cohorts may increase the maintenance doses to 20 mg/kg SYNT001, which the model predicts will achieve greater IgG reductions between approximately 55% and 72%. Given the rigorous biological approach taken in the development of the model, simulations of dosing schedules can be considered reliable for the purpose of planning clinical trials.

Several recently completed non-clinical studies support the proposed Cohort 2 dose and dosing regimen. A recently completed 27-week dose-response good laboratory practice (GLP) toxicology study in non-human primates assessed the long-term safety, toxicology, and

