2. STUDY OBJECTIVES AND ENDPOINTS

2.1.1 Primary Objective and Endpoint

Primary Objectives	Primary Endpoints
Safety: To evaluate the safety and tolerability of IV infusions of SYNT001 at different dose levels and dosing regimens in subjects with WAIHA	Safety: The evaluation of SYNT001 safety based on vital signs, physical examinations, electrocardiograms (ECGs), clinical safety laboratory tests, the incidence of adverse events (AEs), treatment-emergent adverse events (TEAEs), and serious adverse events (SAEs) summarized by dose and dosing regimen, severity, and relationship to study drug

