3. STUDY OVERVIEW

3.1 Overview of Study Design

This is a multicenter, open-label study to assess the safety, tolerability, efficacy, PK, PD, and immunogenicity of SYNT001 IV administered to subjects with WAIHA.

Up to 8 subjects with a diagnosis of WAIHA will receive SYNT001 10 mg/kg weekly x 5 doses (Cohort 1). Up to 12 subjects with a diagnosis of WAIHA will receive SYNT001 (10, 20 or 30 mg/kg) weekly x 3 doses (Loading), followed by SYNT001 (10, 20 or 30 mg/kg) every other week x 5 doses (Maintenance) or SYNT001 (10, 20 or 30 mg/kg) weekly x 10 doses (alternative weekly maintenance schedule) (Cohort 2). An overview of the study cohorts is provided in Table 1.

Table 1. Cohort Overview

Cohort	No. of subjects	SYNT001 Dose	No. of Doses	Frequency of Doses
1	Up to 8	10 mg/kg	5	Weekly
2	Up to 12	Loading: 10, 20 or 30 mg/kg Maintenance: 10, 20 or 30 mg/kg	3 5	Weekly Every other week
2 Alternative weekly schedule	Up to 12	Loading: 10, 20 or 30 mg/kg Maintenance: 10, 20 or 30 mg/kg	3 10	Weekly Weekly

Subjects in both cohorts will complete the following periods of assessment: Screening, Treatment, and Follow-Up. For Cohort 1 details of the dosing schedule and assessments, see Appendix [Table 2](#). For Cohort 2 details, see Appendix [Table 3](#). An alternative weekly maintenance schedule of assessment for Cohort 2 is presented in Appendix [Table 4](#).

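### Adverse events are tabulated only by cohort over the whole study, so when Cohort 2 loading and maintenance doses differ, no AE table relates an event to the dose level at onset

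*SAP*

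**What the plan says.** The primary objective in SAP 2.1.1 is "To evaluate the safety and tolerability of IV infusions of SYNT001 at different dose levels and dosing regimens in subjects with WAIHA". The matching endpoint, repeated in Protocol 11.5, has AEs, TEAEs and SAEs summarized by dose and dosing regimen, severity and relationship.

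SAP 4.1 treats dose and dosing regimen as the same thing as cohort, and SAP 4.7 follows: "The incidence of AEs, TEAEs and SAEs will be summarized by cohort, severity and relationship to study product". The TEAE definition in SAP 4.7.1 covers an event that starts, or "worsens in severity on or after the first dose of study drug, during the treatment period and follow-up period". The tables listed there are by system organ class, preferred term, grade and relatedness, with infusion-related reactions shown separately. A subject counts once per preferred term, at the worst grade.

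Cohort and dose level are not the same thing in Cohort 2. SAP 3.1 gives "Loading: 10, 20 or 30 mg/kg Maintenance: 10, 20 or 30 mg/kg". The doses are fixed only after the Cohort 1 review, but Protocol 2.2 states: "This regimen of 30 mg/kg loading doses and 10 mg/kg maintenance doses was determined to be the optimal starting regimen".

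**The concern.** A subject on a 30/10 regimen spends part of the study at one dose level, a longer part at another, and the rest off drug. The cohort column adds these together. An event after the third 30 mg/kg infusion, one after the fourth 10 mg/kg infusion and one in late follow-up all enter the same figure. This is so even if all 12 Cohort 2 subjects receive the identical regimen.

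At stake is whether the report can describe AE experience by dose level, which the primary objective names. No test, sample size or error rate is affected, since all safety analysis is descriptive.

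**Working it through.** The plan gives no AE rate, alpha or power, so it has no figure of its own to reproduce. The check has three parts: the AE outputs, the schedule, and the form the added table would need.

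**1. Which safety outputs separate loading from maintenance?**

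| Output | Grouping in the SAP | Phases separable? |
|---|---|---|
| AE tables (4.7, 4.7.1) | cohort, severity, relationship, term | no |
| Laboratory (4.7.2) | cohort, visit, time point | yes |
| Physical examination (4.7.3) | visit, dose | yes |
| Vital signs, ECG (4.7.3) | cohort, time point | yes |
| AE listings (4.7.1), dosing listings (4.6) | by subject | only by hand |

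No rule assigns an AE to a phase or to the last dose before onset. Appendix B mentions a post-treatment AE category, but 4.7.1 neither defines nor tabulates one.

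**2. What does the cohort column pool?** Three loading levels times three maintenance levels give 9 pairs; 3 are equal, so 6 differ within a subject. Taking the 30/10 example with the visit days in SAP Tables 3 and 4:

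- Every other week: first maintenance infusion Day 28, end of study Day 140. Share of window before maintenance: 28/140 = 20%. Loading exposure: 3 × 30 = 90 mg/kg; maintenance: 5 × 10 = 50 mg/kg; 90/140 = 64%.
- Weekly alternative: first maintenance infusion Day 21. Share: 21/140 = 15%. Maintenance: 10 × 10 = 100 mg/kg; 90/190 = 47%.

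**3. Would a plain percentage by phase repair this?** Let maintenance run to 14 days after the last infusion (Day 84 + 14 = Day 98). It then lasts 98 − 28 = 70 days every other week, or 98 − 21 = 77 days weekly. As an illustration only, assume a daily risk of a first event within a phase of 1% in maintenance and a multiple of that in loading. Incidence is 1 − (1 − p)^days.

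| Schedule | Loading risk | Loading | Maintenance |
|---|---|---|---|
| Every other week | 3% per day | 1 − 0.97^28 = 57.4% | 1 − 0.99^70 = 50.5% |
| Every other week | 2% per day | 1 − 0.98^28 = 43.2% | 50.5% |
| Weekly | 3% per day | 1 − 0.97^21 = 47.3% | 1 − 0.99^77 = 53.9% |

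A tripled daily risk shows as a 7-point gap on the first schedule and is reversed on the weekly one. A doubled risk is reversed on the first. With 0.5% per day tripled, the every-other-week figures are 34.5% and 29.6%.

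Rates per subject-time avoid this. In the first row, expected event-free days at risk per subject are 0.574/0.03 = 19.1 in loading and 0.505/0.01 = 50.5 in maintenance. The rates are therefore 0.574/19.1 = 3.0 and 0.505/50.5 = 1.0 per 100 subject-days, which recovers the threefold ratio.

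**The case against.** The strongest reply has four parts.

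- **No breach of the endpoint.** Loading followed by maintenance is itself a dosing regimen. The PD, PK and disease-marker endpoints add time point, and the safety endpoint does not. This stands: a reader might infer that the SAP breaks a promise to tabulate by phase, but no such promise is made. What remains is that the objective names dose levels and the AE tables cannot show them when the doses differ.
- **Much is available elsewhere.** With at most 12 subjects, AE and dosing listings let a reader date each event. Infusion-related reactions are tabulated separately, table shells are in separate documents (SAP 6), and SAP 1 allows supplementary analyses. This lowers the importance of the point, but a listing is not a summary and no derivation is specified.
- **Dose at onset is not clean attribution.** Loading always comes first. Protocol 2.2 simulates the IgG nadir between Days 21 and 28, with a 50% to 68% reduction maintained afterwards, so an event early in maintenance may reflect loading exposure. This stands and must be stated with the table.
- **The point is conditional.** Cohort 2 doses are chosen later, and 3 of the 9 pairs are equal. Safety during the trial rests on the 24-hour, 7-day and ongoing reviews and the stopping rules, not on final tables. This also stands.

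**Conclusion.** The point holds for AE tables, when Cohort 2 loading and maintenance doses differ. It is a cheap improvement to a descriptive analysis. The size that the documents support is one of exposure: at 30/10 mg/kg every other week, a fifth of the window carries 64% of the mg/kg given, and the AE column does not distinguish that fifth. This rests on the Protocol 2.2 regimen as an example, since the Cohort 2 doses are not fixed.

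Two stronger readings are tempting and not supported.

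- A reader might infer that no safety table separates the dose levels. The laboratory, physical examination, vital sign and ECG summaries do, by visit or time point.
- A reader might put a number on the dilution by assuming an excess risk in loading and comparing incidence with and without it. With 1% per day tripled, that gives 57% versus 25% within loading and 86% versus 76% over the study. The comparison is with the same subjects free of the excess, which an open-label cohort cannot observe, and the rates are not in the documents. What a table could show is loading beside maintenance, and part 3 of the working shows how far that differs.

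**What to change.** In SAP 4.7.1, keep the whole-study tables and add one descriptive table of TEAEs, related TEAEs, Grade 3 or higher TEAEs and SAEs by phase at onset.

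- **Cohort 2:** loading (first infusion to just before the first maintenance infusion), maintenance (to 14 days after the last infusion) and follow-up.
- **Cohort 1:** treatment (to 14 days after the last infusion) and follow-up.
- **Labels:** the mg/kg dose given in each phase.
- **For each phase:** number of subjects entering it, as the denominator; subject-days at risk; events and first-event incidence per subject-time.
- **Denominator rule:** subjects who stop during loading do not count in the maintenance denominator.
- **Footnote:** phase is confounded with time, order and carry-over.

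The 14-day boundary matches the period in Protocol 6.10 during which WAIHA treatment and corticosteroids are to stay stable.

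The table uses AE onset dates and infusion dates already collected, and changes no sample size or clinical rule. The cost is SAP wording, one extra table set and small counts per cell.
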